#### 10.8.5.1.5. Relationship

The Investigator is obligated to assess the relationship (causal relationship) between the study treatment and each occurrence of each adverse event. The adverse event relationship (causal relationship) to study treatment must be characterized as one of the following categories:

Not Related:	The adverse event does not follow a reasonable temporal sequence from administration of the drug, does not abate upon discontinuation of the drug, does not follow a known or hypothesized cause-effect relationship, and (if applicable) does not reappear when the drug is reintroduced, furthermore, there may exist a clear alternative medical explanation (eg, underlying disease state) or association with study procedure or study conduct.
Unlikely Related:	The temporal association between the adverse event and the drug is such that the drug is not likely to have any reasonable association with the adverse event.
Probably Related:	The adverse event follows a reasonable temporal sequence from administration of the drug and cannot be reasonably explained by the known characteristics of the subject's clinical state, environmental, or toxic factors, or other modes of therapy administered to the subject.
Related:	The adverse event follows a reasonable temporal sequence from administration of the drug, abates upon discontinuation of the drug, follows a known or hypothesized cause-effect relationship, and (if appropriate) reappears when the drug is reintroduced.

The Investigator will use clinical judgment to determine the relationship. Alternative causes, such as underlying disease(s), concomitant therapy, and other risk factors, as well as the temporal relationship of the event to the study treatment administration should be considered and investigated. The Investigator should consult the IB and the Product Information of marketed products within the drug class, when applicable. For each adverse event, the Investigator must document in the medical notes that he/she has reviewed the adverse event and has provided an assessment of causality. There may be situations in which an SAE has occurred, and the Investigator should always make an initial assessment of causality for every event before the initial transmission of the SAE to the Sponsor. The Investigator may change his/her opinion of causality based on subsequent receipt of information and send an SAE follow-up report with the updated causality assessment. The causality assessment is one of the criteria used when determining regulatory reporting requirements.

#### 10.8.5.2. Eliciting, Recording, and Reporting Adverse Events

#### 10.8.5.2.1. Eliciting Adverse Events

Subjects will be instructed that they may report adverse events at any time. An open-ended or nondirected method of questioning should be used at each study visit to elicit the reporting of adverse events.

#### **10.8.5.2.2. Recording Adverse Events**

The adverse event reporting period for safety surveillance begins when the subject is initially included in the study (date of first signature of informed consent) and continues up to 30 days after the last study treatment administration. If an adverse event is not resolved or stabilized by this time, the Sponsor in consultation with the Investigator will decide whether or not further follow-up is necessary.

Investigator and study personnel will record all adverse events and SAEs whether received through an unsolicited report by a subject, elicited during subject questioning, discovered during physical examination, laboratory testing, and/or other means by recording them on the eCRF and SAE Report Form, as appropriate. The following information should be recorded on the adverse event eCRF:

- Description including onset and resolution dates
- Whether it met SAE criteria
- Severity
- Relationship to study treatment or other causality
- Outcome

Any SAE suspected to be related to the study treatment must be reported whenever it occurs, irrespective of the time elapsed since the last study treatment administration.

For SAEs, events occurring secondary to the primary event should be described on the SAE Report Form in the narrative description of the case.

The following should be considered when recording SAEs:

- Death is an outcome of an event. The event that resulted in the death should be recorded and reported on both an SAE Report Form and eCRF.
- For hospitalizations, surgical, or diagnostic procedures, the illness leading to the surgical or diagnostic procedure should be recorded as the SAE, not the procedure itself. The procedure should be captured in the narrative as part of the action taken in response to the illness.

#### 10.8.5.2.3. Diagnosis Versus Signs or Symptoms

In general, the use of a unifying diagnosis is preferred to the listing out of individual symptoms. Grouping of symptoms into a diagnosis should only be done if each component sign and/or symptom is a medically confirmed component of a diagnosis as evidenced by standard medical textbooks. If any aspect of a sign or symptom does not fit into a classic pattern of the diagnosis, report the individual symptom as a separate adverse event.

#### 10.8.5.3. Reporting Serious Adverse Events

All SAEs are subject to reporting requirements.

#### 10.8.5.3.1. Serious Adverse Events

All SAEs, whether or not considered related to study treatment, must be reported to the Sponsor Contact **within 24 hours of becoming aware of the event**. In addition, a completed report using the Sponsor's SAE Report Form must be submitted within 24 hours of notification to the designated Sponsor Contact.

IQVIA Pharmacovigilance [contact]

[contact]

#### Email (preferred method): [contact]

If additional follow-up information is required or becomes available for a previously reported SAE, the new information should be reported to the designated Sponsor Contact within 24 hours of awareness.

Elective hospitalization and/or surgery for clearly preexisting conditions (eg, a surgery that has been scheduled prior to the subject's entry into the study) will not be reported as an SAE. All other hospitalizations, including elective hospitalizations for any condition that was not preexisting, will be reported as an SAE.

Any SAE that is ongoing when the subject completes the study or discontinues the study will be followed by the Investigator until the event resolves, stabilizes or returns to baseline status.

#### 10.8.5.3.2. Serious, Unexpected Adverse Drug Reactions

All ADRs that are both serious and unexpected are subject to expedited reporting to regulatory agencies and will be reported in accordance with Directive 2001/20/EC or as per national regulatory requirements in participating countries. An unexpected ADR is one for which the nature or severity is not consistent with information in the relevant source documents.

The following documents or circumstances will be used to determine whether an adverse event/ADR is expected:

- For a medicinal product not yet approved for marketing in a country, the Reference Safety Information (RSI) section of a company's IB will serve as the source document in that country.
- Reports that add significant information on specificity or severity of a known, already documented serious ADR constitute unexpected events. For example, an event more specific or more severe than described in the RSI in the IB would be considered "unexpected".

#### 10.8.6. Pregnancy

If at any point any pregnancy test is positive, the subject will be withdrawn from the study treatment.

Details of all pregnancies in female subjects and female partners of male subjects will be collected after the start of study treatment and until 90 days after the last dose.

Pregnancy (during maternal or paternal exposure to study treatment) does not meet the definition of an adverse event; however, to fulfill regulatory requirements, any pregnancy and/or pregnancy outcome should be reported via the Pregnancy Report Form to the designated Sponsor Contact (IQVIA) within 24 hours of awareness.

Abnormal pregnancy outcomes (eg, spontaneous abortion, fetal death, stillbirth, congenital anomalies, ectopic pregnancy) are considered SAEs and should be reported as such even if outside the SAE reporting period.

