#### **3.2.2.** Study Population

The study population consisting of subjects with SSc-RP was chosen as representative of the target population. However, subjects with active (or recurrent) skin ulcerations were excluded to avoid the additional burden associated with performing cold challenges, as well as potentially confounding the blood flow assessments. Subjects with advanced multiorgan disease, in particular gastrointestinal dysfunction, have been excluded due to the potential for delayed and/or poor absorption of temanogrel. Although embryo-fetal development studies have not been completed for the temanogrel program, women of child-bearing potential (WOCBP) will be included in the study population. Considering SSc occurs in women approximately 5 to 10 times more frequently than in men (Bergamasco 2019, Lo Monaco 2011), it would be difficult to effectively meet study objectives and perform a representative assessment without the inclusion of WOCBP in this population. In accordance with FDA Guidance for Industry, M3(R2)Nonclinical Safety Studies for the Conduct of Human Clinical Trials and Marketing Authorization for Pharmaceuticals (FDA 2010), inclusion of WOCBP is acceptable because the study is of short treatment duration (less than 2 weeks). In addition, participants who are of child-bearing potential will practice effective control of pregnancy risk and will undergo urine pregnancy testing prior to treatment administration on each Treatment Visit day and a home urine pregnancy test will be administered as part of the final Follow-Up Visit. Serum pregnancy testing will be performed prior to study enrollment and at each Treatment Visit.

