## 9.2. Treatment Visits

Randomization can occur after confirmation of all inclusion and exclusion criteria at Check-in prior to the planned administration of study treatment on Treatment Visit 1.

Each subject will participate in 3 Treatment Visits, which will each be separated by a Washout Period of at least 72 hours and up to approximately 7 days between study treatment administrations. When possible, it is preferred to schedule Treatment Visits with the minimum possible Washout Period between visits. For each Treatment Visit, subjects will be admitted to the clinic at approximately the same time of the day (between 0800 and 1200 hours). A schematic of Treatment Day assessments and procedures is provided in Appendix 2. Refer to the Schedule of Assessments (Appendix 1) for additional details on study assessments and procedures.

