#### 10.2.8. Pregnancy Testing

A serum pregnancy test for beta-human chorionic gonadotropin ( $\beta$ -hCG) will be performed on WOCBP at screening to determine eligibility and at each Treatment Visit. At each treatment visit, urine pregnancy tests ( $\beta$ -hCG) will be performed, and a negative result is required to be documented, prior to administration of study treatment. The results of the serum pregnancy test

at each Treatment Visit are not required prior to dosing. If at any point there is a case of a positive urine  $\beta$ -hCG test, the subject will have study treatment interrupted. If the serum test confirms positive, the subject will be discontinued from the study treatment and all the necessary follow up will be conducted as per Section 10.8.6. If the serum test is negative, the subject may resume study treatment.

At Treatment Visit 1, WOCBP will also be provided with a urine pregnancy test that is to be taken at home prior to the subject's Follow-Up visit on the same day of the Follow-Up visit. During the first Treatment Visit subjects will receive adequate training on the use of the home pregnancy test and will be informed on how to properly communicate the results of their test. If the result of the home pregnancy test is positive, subjects will be required to undergo a serum pregnancy test. If the serum test confirms positive, all necessary follow-up will be conducted as per Section 10.8.6. If the serum test is negative, no further follow-up is required.

Women who are surgically sterile or who are postmenopausal are not considered to be of child-bearing potential. Postmenopausal is defined as 12 consecutive months with no menses without an alternative medical cause.

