#### **10.8.4.** Clinical Laboratory Assessments

Details regarding clinical laboratory sample collection, preparation, and shipment are provided in the laboratory manual. Unless otherwise specified, all laboratory assessments required by the protocol will be performed by a central laboratory. Refer to Table 2 for the list of clinical laboratory tests to be performed and the Schedules of Assessments (Appendix 1) for timing and frequency for each test.

The Investigator must review the laboratory reports, document the review, and record any clinically relevant changes on the adverse event section of the eCRF. The laboratory reports must be filed with the source documents. Clinically significant abnormal laboratory findings are those that are not associated with the underlying disease, unless judged by the Investigator to be more severe than expected for the subject's condition. All laboratory tests with values considered clinically significantly abnormal during participation in the study should be repeated until the values return to normal or Baseline or are no longer considered clinically significant by the Investigator or Medical Monitor.

In cases when laboratory values from nonprotocol-specified assessments are performed at the institution's local laboratory and result in a change in subject management or are considered clinically significant by the Investigator (eg, adverse event or study treatment discontinuation), then the details must be documented in the appropriate eCRF.

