## Table 2:Clinical Laboratory Tests

Pregnancy Testing a	Coagulation	Virology Screening				
Serum pregnancy test beta-human chorionic gonadotropin (β-hCG)	Activated partial thromboplastin time (PTT)	e Hepatitis C virus				
Urine β-hCG	Fibrinogen					
	International Normalized Ratio (INR)	)				
	Prothrombin time (PT)					
	Thrombin time (TT)					
Urinalysis	Hematology					
Appearance	Hematocrit					
Bilirubin	Hemoglobin					
Color	Mean corpuscular hemoglobin (MCH	I)				
Glucose	Mean corpuscular hemoglobin concer	ntration (MCHC)				
Ketones	Mean corpuscular volume (MCV)					
Leukocyte esterase	Platelet count					
Microscopic examination of sediment	Red blood cell (RBC) count					
Nitrite	White blood cell (WBC) count with differential					
Occult blood						
рН						
Protein						
Specific gravity						
Urobilinogen						
Serum Chemistry		Endocrinology				
Alanine aminotransferase (ALT)	Phosphorus	Thyroid-stimulating hormone				
Albumin	Potassium	(TSH)				
Alkaline phosphatase (ALP)	bouldin	hyroxine (T4) free				
Aspartate aminotransferase (AST)	Total bilirubin	Triiodothyronine (T3) free				
Bicarbonate	Total cholesterol					
Blood urea nitrogen (BUN)	Total protein					
Calcium	Triglycerides					
Chloride	Uric acid					
Creatinine						
Direct bilirubin						
Creatine kinase (CK)						
Glucose						
Lactate dehydrogenase (LDH)						

Biomarkers
Endothelin-1
Factor VIII activity
Intracellular adhesion molecule 1 [ICAM-1]
Plasminogen activator inhibitor-1 [PAI-1] activity
PAI-1 antigen
Serotonin
Tissue-type plasminogen activator antigen [t-PA]
Vascular adhesion molecule 1 (VCAM-1)
Vascular endothelial growth factor (VEGF)
Von Willebrand factor [VWF]
Urine Drug Screen
Amphetamines, barbiturates, benzodiazepines, cocaine, marijuana, methadone, methamphetamine,

methylenedioxymethamphetamine, opiate, oxycodone, phencyclidine

a Required only for women of child-bearing potential.

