c The Screening Period will last for up to 28 days prior to Treatment Visit 1 (Day -28 to 1).

d Predose assessments are to occur on each Treatment Visit at approximately the same time of the day after the subject has acclimatized for at least 20 minutes in a temperature-controlled room (23 [± 1]°C).

- e Postdose assessments are to occur at each Treatment Visit at 45 (± 5) minutes after study treatment administration and re-acclimatization for at least 20 minutes in a temperature-controlled room (23 [± 1]°C).
- f Subjects are required to undergo acclimatization for at least 20 minutes in a temperature-controlled room (23 [± 1]°C) and IR thermography is used to assess digit temperature to determine eligibility.

g A full physical examination is performed per the site's standard of care at Screening. A symptom-based physical exam is performed at the end of final Treatment Visit (Treatment Visit 3).

h An exam of the hands for digital ulcers is performed at each Treatment Visit at Check-in.

i Postdose PK and biomarkers blood samples will be collected after the post-cold challenge digital blood flow assessment are completed. Refer to Section 10.5 for further information on blood sample collection.

j Pregnancy tests are required for all women of child-bearing potential. A serum pregnancy test is performed at Screening to determine eligibility and at each Treatment Visit. Urine pregnancy tests with a negative result are required prior to dosing at each Treatment Visit. Results of the serum pregnancy test at each Treatment Visit are not required prior to dosing. A home pregnancy test will be performed as part of the Follow-Up Visit.

k Urine drug screen at Screening is performed to determine eligibility. The results of subsequent urine drug screens are not required prior to initiating study conduct of each Treatment Visit. However, if at any time a subject test positive for any drug included in the urine drug screen, the subject may be discontinued from study treatment at the discretion of the Sponsor.

 The first day of the most recent menstrual cycle is documented at each Treatment Visit at Check-in.

[figure not shown]
m Subjects will be asked about their adherence to restrictions described in Section 5. Responses will be documented in the eCRF.

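### Sections 10.8.6 and 10.2.8 give opposite instructions for a urine-positive, serum-negative subject; secondarily, no deadline ties a visit's serum pregnancy result to the next dose

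*Combined protocol and SAP*

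**What the plan says.** **After a positive test.** Section 10.8.6 opens: "If at any point any pregnancy test is positive, the subject will be withdrawn from the study treatment". It covers every pregnancy test and has no confirmation step. Section 10.2.8 describes the testing procedure. A positive urine test interrupts treatment, a confirming serum test leads to discontinuation with follow-up under 10.8.6, and otherwise "If the serum test is negative, the subject may resume study treatment".

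**Timing of the serum test.** Women of child-bearing potential have a serum test at screening and at each Treatment Visit, and need a documented negative urine test before every dose. Appendix 1, footnote j, adds: "Results of the serum pregnancy test at each Treatment Visit are not required prior to dosing". Section 10.2.8 says the same.

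**Review of results.** Section 10.8.4 says: "The Investigator must review the laboratory reports, document the review". Table 2 includes "Serum pregnancy test beta-human chorionic gonadotropin" among the tests. Section 10.8.4 gives no time limit. Section 10.2 requires review before dosing only for screening evaluations and the first dose.

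**Spacing of doses.** Section 9.2 has Treatment Visits "separated by a Washout Period of at least 72 hours and up to approximately 7 days between study treatment administrations", and adds: "When possible, it is preferred to schedule Treatment Visits with the minimum possible Washout Period between visits".

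**Background.** Section 3.2.2 notes that "embryo-fetal development studies have not been completed for the temanogrel program". It supports enrolling these women by the short treatment duration, pregnancy prevention, and urine and serum testing.

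**The concern.** The first issue is a plain conflict. For one combination of results, two operative sections prescribe different dispositions, so a site following either in good faith departs from the other. At stake is the unnecessary loss of a subject from a small crossover: Section 6.4 plans 4 subjects per sequence in each stage, and the Per Protocol Set in Section 11.3 requires all 3 doses.

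The second issue is smaller and concerns safety. A serum sample drawn at one visit can protect against the next dose only if its result has been seen by then. The protocol cites serum testing at each visit in support of enrolling women of child-bearing potential, but does not link the result to any later dose.

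**Working it through.** **1. The two rules side by side**

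| Urine | Serum | Section 10.8.6 | Section 10.2.8 | Agreement |
|---|---|---|---|---|
| + | + | Withdraw | Discontinue, follow up per 10.8.6 | Yes |
| + | − | Withdraw | May resume | **No** |
| − | + | Withdraw once known | No express rule during treatment | 10.8.6 applies |
| − | − | Continue | Continue | Yes |

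Only the second row conflicts. Section 10.2.8 points to 10.8.6 solely for follow-up after a confirmed positive, and 10.8.6 contains no exception pointing back. Section 8.1 lists pregnancy as a reason for discontinuation and cites only 10.8.6. Section 6.3.2 says that dose interruptions will not occur, which does not fit the interruption in 10.2.8.

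**2. When the next dose could precede the serum result**

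This concerns only the third row. To receive a further dose, the subject must be serum-positive at one visit and urine-negative both then and at the next visit, at least 72 hours later.

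Inputs: washout W is 3 to about 7 days (Section 9.2). Turnaround T is not stated, so a range of 1 to 5 days is assumed, with review as soon as the result arrives.

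- The next dose precedes the result only if T > W.
- At W = 3 days this happens for T above 3 and up to 5 days.
- At W of 5 days or more it cannot happen within the assumed range.
- The earliest Visit 3 dose falls 72 + 72 = 144 hours = 6 days after the Visit 1 dose. Since 6 > 5, a Visit 1 result is available before Visit 3.

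Under these assumptions at most one further dose can precede a result. If T exceeds 6 days, or an available result is not read, this bound fails, and a Visit 1 positive could be followed by both remaining doses, provided the urine test stays negative.

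**3. What that dose would be**

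Section 6.4 gives six sequences, with A the higher dose, B the lower dose and C placebo.

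| Sequence | Period 2 | Period 3 |
|---|---|---|
| ABC | B | C |
| ACB | C | B |
| BAC | A | C |
| BCA | C | A |
| CAB | A | B |
| CBA | B | A |

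Each period has 2 A, 2 B and 2 C, so the dose is active in 4 of 6 sequences after either visit. In Stage A, A is 120 mg and B is 60 mg. In Stage B the ceiling is 240 mg (Section 3).

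**4. Delay from waiting for the result**

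Largest delay in the assumed range: 5 − 3 = 2 days. Slack in the washout window: 7 − 3 = about 4 days. A turnaround above about 7 days would push the visit outside the window.

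The documents give no basis for estimating how many subjects would be affected by either issue.

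**The case against.** On the conflict, one can read the sections together: 10.2.8 governs confirmation and 10.8.6 governs what follows a confirmed pregnancy. That is a sensible reading and is the reason for resolving the conflict in favour of 10.2.8. It is not what 10.8.6 says, however, and no precedence rule is stated. It is also fair that neither reading is unsafe, since a urine-positive subject is not dosed and resumption requires a negative serum result. Lost data may be partly recovered, because Section 6.4 lets the sponsor replace a discontinued subject in the same sequence.

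On timing, the protocol deliberately relies on a negative urine test before each dose and treats serum as an added layer, alongside a screening serum test and highly effective contraception. Turnaround and alert rules may sit in the laboratory manual. All of this stands and keeps the point secondary.

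A reader might infer that the protocol permits dosing of a woman known to be pregnant, or that serum results need never be read. It does neither: 10.8.6 requires withdrawal once a positive is known, and 10.8.4 requires review of laboratory reports. What is missing is only an explicit deadline. A reader might also take the one-dose limit as a property of the design. It depends on the assumed turnaround and on prompt review.

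Finally, the Note to File (Amendment 1) records that enrollment ended after the decision of 25 August 2022 and that the database was locked on 13 October 2022. A correction now mainly helps in interpreting the record and in any reuse of this text.

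**Conclusion.** The conflict is established on the text alone. For a urine-positive, serum-negative subject, 10.8.6 requires withdrawal and 10.2.8 allows resumption. The consequence is inconsistent site practice and possible loss of crossover data, not an unsafe dose.

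The missing deadline is also established as an absence from the protocol, but it is a lesser point. It concerns only a subject who is serum-positive at one visit and urine-negative at that visit and the next, and an operational rule may exist in the unseen laboratory manual. With an assumed turnaround of 1 to 5 days and prompt review, at most one further dose could precede the result, active in 4 of 6 sequences, up to 120 mg in Stage A and up to 240 mg in Stage B. With longer turnaround or late review that bound does not hold.

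Neither issue bears on power or Type I error. Both are minor, optional corrections.

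**What to change.** 1. Replace the opening sentence of Section 10.8.6 with: *If any serum pregnancy test is positive, the subject will be withdrawn from study treatment. A positive urine test interrupts study treatment as described in Section 10.2.8.* This follows 10.2.8 because that section is the specific testing procedure and already requires a negative serum test before resumption. Align Section 6.3.2 by allowing for the interruption in 10.2.8.

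2. In Section 10.2.8 and Appendix 1, footnote j, after the sentence on serum results and dosing, add: *The serum result from the preceding Treatment Visit must be reviewed and negative before the next dose.* Check the laboratory manual for an existing turnaround or alert rule and keep the two consistent.

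The cost is a few sentences, with no new test, sample or visit. The first change gives up the stricter literal rule in 10.8.6, with the negative serum test as the remaining protection. The second may delay Visit 2 or Visit 3 when a result is late, by up to about 2 days under the assumed turnaround, which stays inside the washout window.
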